To address **Aim 1** (*impact of menopause-related sleep fragmentation on metabolic and behavioral biomarkers of body fat gain*), the mean levels in each endpoint in response to experimentally fragmented sleep (**Hypothesis 1a & 1b**) will be examined using repeated-measures generalized linear mixed-model regression. Models will incorporate the 2 SB contrasts addressing **Hypothesis 1a and 1b** to simultaneously compare the impact of sleep fragmentation in the HF-free, estrogenized environment (**SB_{SF1} vs. SB_{UD1}**), and hypo-E2 environment with stable HF levels (**SB_{SF2} vs. SB_{UD2}**); exploratory analyses will adjust for HF, either categorized (e.g., any versus none) or number of HF. If there is an omnibus effect of experimental sleep fragmentation, we will conduct post-hoc analyses on each SB contrast to explore whether the impact of experimental sleep fragmentation is consistent across hormonal and HF contexts. To address **Hypothesis 1c**, mean levels in outcomes will be contrasted **SP_{UD3} vs. SP_{UD1}** to assess the impact of sleep disruption related to HF in the environment without experimental sleep fragmentation, comparing those developing HF (expected N=26) with those who do not develop HF; analyses will adjust for initial E2 level.

Aim 2 (*impact of HF on metabolic and behavioral biomarkers of body fat gain*) will be examined using a repeated-measures generalized linear mixed-model regression analysis to determine the effect of HF on mean levels of in metabolic and behavioral biomarkers. The regression will include SB contrasts that assess the impact of HF in the presence (**SB_{SF2} vs. SB_{SF1}**) and absence (**SB_{UD2} vs. SB_{UD1}**) of experimental sleep fragmentation. If an omnibus effect of HF is observed, post-hoc analyses will be conducted on each SB contrast to explore whether the impact of HF is consistent across sleep fragmentation contexts. Additional analyses will substitute objectively measured HF or night-time only HF.

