To address **Aim 3** (*impact of estradiol withdrawal on metabolic and behavioral biomarkers of body fat gain*), the mean levels in each endpoint in response to estradiol withdrawal (**Hypothesis 3**) will be examined using repeated-measures generalized linear mixed-model regression. Models will incorporate the 2 estrogenized and hypo-E2 contrasts addressing simultaneously the impact of estradiol withdrawal in the unfragmented and fragmented sleep states. If there is an omnibus effect of estradiol withdrawal, we will conduct post-hoc analyses on each sleep state contrast to explore whether the impact of estradiol withdrawal is consistent across both sleep states. Exploratory analysis will include adjusting for HF – either categorical (yes/no or

none/infrequent/frequent) or continuous – and sleep HF-related disruption in the hypo-E2 state (second SB).

Exploratory Hypothesis #1 analyses will involve a repeated-measures generalized linear mixed-model regression similar to those proposed for the **Hypothesis 1a** analysis using the RQ as an indirect measure of resting EE as the dependent measure, and the same post-hoc paired contrasts and interaction terms for randomization order. **Exploratory Hypothesis #2** analyses will involve addition of interaction terms (between total body fat or visceral adiposity with sleep fragmentation, HF, or E2 withdrawal) to models described for **Aims 1–3**, to test for effect modification on each metabolic or behavioral endpoint. These analyses are by necessity exploratory in nature given the sample size of this complex experimental study. **Exploratory Hypothesis #3** will involve an omnibus repeated-measures regression model encompassing all 6 contrasts described in **Aims 1–3** with the PANAS Negative Affect scale score as the primary predictor and adjustment for fragmented versus undisturbed sleep given an expected association between sleep fragmentation and affect. Post-hoc analyses using paired t-tests on each SB contrast will be conducted to explore the potential variability of the impact of negative affect on each metabolic and behavioral biomarker across the sleep fragmentation, HF, and hormonal contexts. Psychological and cognitive factors driving eating behaviors on the DEBQ will also be explored.

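### Aim 2's hot-flash contrasts and post-hoc tests are the same block differences that Aim 3 uses for estradiol withdrawal, so they cannot show a hot-flash effect

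*SAP*

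**What the plan says.** Labels: SF is fragmented and UD undisturbed sleep; 1 is the block before leuprolide and 2 the block after it. Aim 1 of the SAP fixes these meanings.

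- **Aim 2, contrasts.** "The regression will include SB contrasts that assess the impact of HF in the presence" (SF2 vs SF1) and absence (UD2 vs UD1) of experimental fragmentation.
- **Aim 2, follow-up.** "If an omnibus effect of HF is observed, post-hoc analyses will be conducted on each SB contrast", in order to explore whether the HF effect is consistent across sleep contexts.
- **Aim 2, other HF measures.** "Additional analyses will substitute objectively measured HF or night-time only HF".
- **Aim 3.** "Models will incorporate the 2 estrogenized and hypo-E2 contrasts addressing simultaneously the impact of estradiol withdrawal in the unfragmented and fragmented sleep states". HF enters only here: "Exploratory analysis will include adjusting for HF".
- **Aim 1.** For Hypotheses 1a and 1b, "exploratory analyses will adjust for HF, either categorized (e.g., any versus none) or number of HF". Hypothesis 1c contrasts undisturbed sleep after and before leuprolide, "comparing those developing HF (expected N=26) with those who do not develop HF; analyses will adjust for initial E2 level".
- **Exploratory Hypothesis 2** lists the modifiers separately: "total body fat or visceral adiposity with sleep fragmentation, HF, or E2 withdrawal".

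In the protocol, Hypothesis 2 (Specific Aims) is about a correlation with HF frequency. The Overview says that leuprolide induces hypo-estrogenism in every woman and HF in about two thirds. Inclusion criterion 6 requires no previous HF, so HF is zero in block 1.

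**The concern.** Aims 2 and 3 read the same two differences as two different causes. The protocol's stated goal, in its section on the importance of the knowledge to be gained, is to isolate hot flashes and estrogen withdrawal from each other. A difference that contains both cannot do this.

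The post-hoc step is where the plan as written can go wrong. Suppose HF affects an outcome only in undisturbed sleep, while estradiol withdrawal affects it in both sleep states. The overall HF test may be correctly significant. The follow-up on SF2 vs SF1 can then be significant because of estradiol alone, and the report would say that the HF effect is consistent across sleep contexts. In addition, the SAP does not say which coefficient tests Hypothesis 2, which HF measure is primary, or whether block is held fixed.

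**Working it through.** **1. The contrasts coincide.** Aim 3 does not print the block labels, so this is an inference. There are two blocks; Aim 1 calls block 1 estrogenized, and Aim 3 calls the hypo-estrogenic state the second block. Over the cells (UD1, SF1, UD2, SF2):

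| Aim | Undisturbed | Fragmented |
|---|---|---|
| 2 | (−1, 0, 1, 0) | (0, −1, 0, 1) |
| 3 | (−1, 0, 1, 0) | (0, −1, 0, 1) |

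The Aim 2 pair has rank 2, and adding the Aim 3 pair leaves it at 2.

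**2. What a block contrast estimates.** Let e be the estradiol effect and h the HF effect. With 26 of 40 women expected to have HF, the mean change is e + (26/40)h = e + 0.65h, plus anything else that changes between blocks. If h = 0, it is still e. A woman-level HF-by-block term is separately estimable: it raises the rank of the design from 4 to 5.

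**3. The plan's own figure.** By Fisher z at two-sided 0.05 and 80% power, r = tanh((1.960 + 0.842)/√(n − 3)). For n = 40 this gives tanh(2.802/6.083) = 0.431, and for n = 26 it gives 0.526. The SAP states 0.43 and 0.52, so its figures reproduce. They come from EEG arousals and leptin, not HF, and do not identify the Hypothesis 2 test.

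**4. Size of the post-hoc problem.** No document gives an estradiol or HF effect, so the effects are assumed, in SD of within-woman block change. Setting: 26 women with HF and 14 without; HF acts only in undisturbed sleep; the two block changes correlate ρ = 0 to 0.5. The overall HF test is taken as block-adjusted: 26 vs 14 on each woman's mean change.

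- *Overall test.* The difference in mean change is h/2, with SD √((1 + ρ)/2). For h = 0.95 this is 0.475/0.707 = 0.67 SD at ρ = 0 and 0.475/0.866 = 0.55 SD at ρ = 0.5. Power is about 51% and 36%.
- *Post-hoc SF2 vs SF1.* A paired t-test with n = 40 is significant in 23%, 46% or 79% of trials at e = 0.2, 0.3 or 0.45, although HF does nothing in fragmented sleep. After a significant overall test, the simulated rates are nearly the same (24–25%, 46–47%, 79–80%; 5% at e = 0).
- *Both together*, by simulation:

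| HF effect (undisturbed only) | e = 0.2 | e = 0.3 | e = 0.45 |
|---|---|---|---|
| 0.95 SD | 9–12% | 18–24% | 29–40% |
| 1.5 SD | 17–21% | 33–40% | 57–70% |

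The ranges run from ρ = 0.5 (low end) to ρ = 0 (high end). Repeat runs agree to about one percentage point; for example, one gave 17% in place of 18%.

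**5. The alternative test.** With no HF effect, and HF unrelated to a woman's estradiol response, the 26 vs 14 comparison of block change rejects in about 5% of trials whatever e is. A mixed model with woman intercepts only does not hold this level: the HF term rejects in about 10% of null trials at ρ = 0.25 and 14% at ρ = 0.5.

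**The case against.** **An HF predictor is the natural reading.** Hypothesis 2 is about frequency, a block contrast contains no HF measure that could be substituted, and Exploratory Hypothesis 2 separates HF from estradiol withdrawal. This stands. A reader might infer that the block contrasts are themselves the Aim 2 test, so that an estradiol effect of 0.2, 0.3 or 0.45 SD would be declared an HF effect in 23%, 46% or 79% of trials with no HF effect at all. The documents do not support that as the main reading, and those rates apply only under it.

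**HF is compared elsewhere.** Hypothesis 1c compares women with and without HF in undisturbed sleep, adjusted for initial estradiol, and is not labelled exploratory. This also stands, so the goal of isolating HF is not unprotected. But Hypothesis 1c does not cover fragmented sleep or HF frequency, and it is not designated as the Hypothesis 2 test.

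**The post-hoc step is gated and exploratory.** It could also mean the association of HF with each block change. That is possible. However, Exploratory Hypothesis 3 describes its own post-hoc tests as paired t-tests on each block contrast, which favours the raw-contrast reading. The gate is a fair reason not to quote the rates conditional on a significant overall test as the error rate. The table gives the unconditional rates.

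**Conclusion.** The point holds in a limited form. Firm: the contrasts labelled as HF contrasts are the estradiol contrasts, they estimate the total leuprolide effect, and post-hoc tests on them cannot show an HF effect or its consistency across sleep contexts. Also firm: the coefficient for Hypothesis 2 is not named. The overall HF test is affected only if the contrasts are themselves that test.

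It would go too far to conclude that Aim 2 has no HF variable or that the trial cannot address Hypothesis 2. HF varies between women in block 2, so an HF association is estimable.

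The percentages rest on assumed effects, on HF acting only in undisturbed sleep, and on a block-adjusted overall test. They show that the misreading can be frequent (9–40% at an HF effect of 0.95 SD, 17–70% at 1.5 SD); they do not predict its rate in this trial. This should be fixed before analysis.

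**What to change.** Change the SAP wording; no new data are needed.

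1. State that Hypothesis 2 is tested by the HF term: HF frequency, zero in block 1, with any/none as an alternative. The mixed model also contains block and fragmentation terms and a woman-level random block effect, and adjusts for initial estradiol as in Hypothesis 1c. An equivalent is to analyse each woman's mean block change. The planned objective and night-time measures then replace this term.
2. Replace the post-hoc tests on the raw block contrasts with an HF-by-fragmentation term.
3. Keep the block contrasts for Aim 3, reported as the total leuprolide effect beside the planned HF-adjusted estimate.
4. Report Aim 2 as an association, because HF is not randomised.

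**Cost.** Precision falls. At 80% power the detectable difference is about 0.95 SD of change for 26 vs 14 women (normal approximation: 2.80 × √(1/26 + 1/14) = 0.93), or |r| of about 0.43 for frequency. The block contrast detects about 0.45 SD, but of a different quantity. The HF-by-fragmentation term compares differences with SD √(2(1 − ρ)), so at 0.95 SD its power is about 50% (ρ = 0) to 80% (ρ = 0.5). HF may still partly track the size of the estradiol fall, so the revised test is not fully protected. Reproductive hormones are measured at each admission, so adjusting for the measured fall is available as an optional sensitivity analysis.

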Document Title: Study Protocol

Protocol Title: Menopausal Sleep Fragmentation: Impact on Body Fat Gain Biomarkers in Women

Protocol #: MGB Human Research Committee #2016P002821

NCT: 03047330

Document date: January 3, 2024

**PARTNERS HUMAN RESEARCH COMMITTEE
PROTOCOL SUMMARY**

Answer all questions accurately and completely in order to provide the PHRC with the relevant information to assess the risk-benefit ratio for the study. Do not leave sections blank.

PRINCIPAL/OVERALL INVESTIGATOR

[name], MSc

PROTOCOL TITLE

Menopausal Sleep Fragmentation: Impact on Body Fat Gain Biomarkers in Women

FUNDING

National Institute of Health – National Institute on Aging

VERSION DATE

1/3/2024

SPECIFIC AIMS

Concisely state the objectives of the study and the hypothesis being tested.

Aim #1: To determine the impact of menopause-related sleep fragmentation on metabolic and behavioral biomarkers of body fat gain using an experimental sleep disruption paradigm to fragment sleep in healthy female volunteers

Hypothesis 1a: Experimental sleep fragmentation will result in an adverse adipokine profile as a metabolic biomarker for body fat gain

Hypothesis 1b: Experimental sleep fragmentation will result in increased hunger and caloric intake

Hypothesis 1c: Sleep disruption due to hot flashes will result in an adverse adipokine profile and increased hunger and caloric intake

Aim #2: To examine if hot flashes are associated with metabolic and behavioral biomarkers of body fat gain using an experimental hormone suppression paradigm in healthy women

Hypothesis 2: Hot flash frequency will correlate with a worse adipokine profile and increased hunger and caloric intake

Aim #3: To determine if estradiol withdrawal adversely affects metabolic and behavioral biomarkers of body fat gain using an experimental hormone suppression paradigm in healthy women

Hypothesis 3: Experimental withdrawal of estradiol will correlate with a worse adipokine profile and increased hunger and caloric intake

Aims 1–3 Exploratory Hypotheses:

1) Experimental sleep fragmentation mimicking menopause-related sleep disruption will reduce resting energy expenditure. 2) Baseline levels of total body fat and visceral adiposity will influence

the metabolic and behavioral response to sleep fragmentation, hot flashes, and estradiol withdrawal. 3) Negative mood state will correlate independently with an adverse adipokine profile and increased hunger and caloric intake.

BACKGROUND AND SIGNIFICANCE

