- Subject will be awakened during the night through auditory stimulus broadcast manually by sleep technicians throughout the night to achieve the target number of awakenings and minutes of Wake After Sleep Onset (WASO) (36 awakenings, 62 minutes WASO). Time In Bed (TIB) will be extended to maintain the 8-hour Total Sleep Time (TST). Auditory tones will be between 2- and 30-seconds duration, beginning at 60 dB and increased to a maximum of 1100db if an EEG awakening is not elicited. Once awake, subjects will be required to stay awake for up to 2 minutes. Subjects will not be permitted to get out of bed or eat in the middle of the night.
- Subjects will be able to order meals and snacks off a provided menu. There will be no dietary restrictions.

Nurses and technicians will be present 24 hours a day, so participants will have frequent social interactions in this controlled setting. Medical and psychologist/psychiatrist evaluation and treatment is available at all times.

Table of Procedures – Study overview

Table of Procedures - All Visits (revised 6/26/2020)						
Study Phase		Pre-Treatment				Post-treatment
Visit Type	Phone/Pre-screen	Screening Visit 1a	Screening Visit 1b	Sleep Block 1	GnRH-a Injection 1	Sleep Block 2
Time from Medication	remote	remote	in-person	in-person	in-person	in-person
General					0	1 week
	Informed Consent	x	x			
	Medical and Psychiatric Interview		x			
	Sleep Interview		x			
	Vitals, exam, & Morphometric measures			x	x	x
	Screening Labs			x		
	Questionnaires (via REDCap survey link)			x		
	Study Medication Administered					x
DXA	DXA Scan				x	
Blood tests	Adipokines				x	x
	Reproductive Hormones			x	x	x
	Metabolic Markers			x	x	x
	Stress			x	x	x
	Monitored Diet				x	x
Sleep Lab Assessments	Food intake/caloric consumption				x	x
	Hunger and Mood Ratings				x	x
	Energy Expenditure				x	x
	Polysomnography				x	x
	Skin Conductance					x
	Body Temperature				x	x
	Reward Behaviors				x	x
	Hot Flash Diaries				x	x
Eligibility Assessments	Sleep diaries				x	x
	Actigraphy Watch				x	x
	Berlin Questionnaire	x				
	PSQI	x			x	x
	ISI	x			x	x
	PHQ-8		x		x	x
	Urine Pregnancy Test				x	x
	PHQ-2	x				
	AE Monitoring		x	x	x	x

Study Endpoints

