Metabolic endpoints are: 1) fasting morning levels of leptin (primary) adipokines, ghrelin (total, acetylated) (secondary), and 2) the circadian leptin profile (exploratory), calculated as area under curve (AUC) to detect whether the overall profile is lower, as seen in sleep restriction studies, and morning fasting AD levels. Behavioral endpoints are: 1) satiety (primary) and hunger (secondary) on a VAS scale, and 2) daily caloric intake during ad lib meals (exploratory). Analyses of each endpoint will be conducted in parallel as we seek to detect coherence among endpoints and focus on consistency across different outcomes in each hormonal and HF context.

For studies involving treatment or diagnosis, provide information about standard of care at Partners (e.g., BWH, MGH) and indicate how the study procedures differ from standard care. Provide information on available alternative treatments, procedures, or methods of diagnosis.

This study involves the administration of leuprolide to healthy individuals in order to better understand experimentally induced hot flashes. Subjects are healthy individuals who do not have any specific medical diagnosis. The DXA scan is not clinically indicated for women participating in the protocol. Alternative imaging studies are therefore not indicated.

Describe how risks to subjects are minimized, for example, by using procedures which are consistent with sound research design and which do not unnecessarily expose subjects to risk or by using procedures already being performed on the subject for diagnostic or treatment purposes.

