Document Title: Statistical Analysis Plan

Protocol Title: Menopausal Sleep Fragmentation: Impact on Body Fat Gain Biomarkers in Women

Protocol #: MGB Human Research Committee #2016P002821

NCT: 03047330

Document date: January 3, 2024

Biostatistical Analysis

Analysis approach: Metabolic endpoints are: 1) fasting morning levels of leptin (primary), adipokines, ghrelin (secondary), and 2) the circadian leptin profile (exploratory), calculated as area under curve (AUC) to detect whether the overall profile is lower, as seen in sleep restriction studies,⁵³ and morning fasting AD levels. Behavioral endpoints are: 1) satiety (primary) and hunger (secondary) on a VAS scale, and 2) daily caloric intake during ad lib meals (exploratory). Analyses of each endpoint will be conducted in parallel as we seek to detect coherence among endpoints and focus on consistency across different outcomes in each hormonal and HF context.

Our experimental design, methodology, and analytic approach are robust and unbiased. While only women will be enrolled, analyses and interpretation of results will take into consideration age and other relevant biological variables. Key covariates will be measured and included as potential predictors in multivariate analyses, including specific *a priori* examination for age, race, BMI, SES, and stressful events to reduce unexplained variability in the outcomes.¹⁴¹ Importantly, within-subject analyses using each woman as her own control and expected low attrition based on our prior experience with similar protocols will minimize potential bias.

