Sample size: Forty subjects will complete all study procedures. Sample size calculations are based on pilot data correlations between the change in the number of EEG arousals and change in leptin levels from before to after receiving GnRHa. The observed Pearson and Spearman correlations are $r=-0.44$ and $r_s=-0.36$. The detectable correlation is $r=-0.43$ for a sample size of 40 and $r=-0.52$ for the subgroup analysis ($n=26$) in **Hypothesis 1c** ($\alpha=0.05$, 80% power). Because it takes 3 months (screening/menstrual tracking plus 2 months of active procedures) for each subject to complete the study and data analysis time is required after all procedures are completed, accrual is expected to be achieved in the first 39–42 months of the Award. The expected accrual rate of 1.1 subjects per month is therefore similar to that which [REDACTED] achieved in prior healthy volunteer studies with a similar number of in-lab nights. This rate is lower than the 1.7/month that [name] achieved with healthy volunteers to leuprolide studies but with less intensive procedures. To ensure that accrual proceeds as planned, we will advertise widely using postcards we have used to enroll 2.4 women/month to menopause studies and which colleagues used to enroll 2.2 healthy volunteers/month to a study with fewer nights in the sleep lab.¹⁴² Based on previous experience, we expect to consent up to 130 subjects in order to have 40 study completers, given that up to 10 women may not be eligible after completing screening procedures and an additional 8 women may decline to receive leuprolide after completing SB#1, and because some women will participate in pilot procedures only.

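### Exploratory Hypothesis 1 predicts lower resting energy expenditure, but the SAP models only the RQ, a ratio that cannot show whether expenditure fell

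*SAP*

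**What the plan says.** The protocol, under Specific Aims (Aims 1–3 Exploratory Hypotheses), states a directional prediction about a quantity: "Experimental sleep fragmentation mimicking menopause-related sleep disruption will reduce resting energy expenditure".

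The SAP's paragraph on the exploratory hypotheses plans a mixed model of the kind used for Hypothesis 1a and specifies its outcome in these words: "using the RQ as an indirect measure of resting EE as the dependent measure". It names no other dependent variable for this hypothesis. It gives no conversion from RQ to energy expenditure and does not say which direction of change in RQ would count as support.

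The protocol's Table of Procedures lists "Energy Expenditure" among the sleep laboratory assessments, with two visit marks, so some measurement of the quantity appears to be planned. Neither document gives its method, unit or derived variable. The endpoint lists (Study Endpoints in the protocol, Analysis approach in the SAP) cover leptin and its circadian profile, other adipokines, ghrelin, satiety, hunger and caloric intake. Neither energy expenditure nor RQ is among them.

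**The concern.** The hypothesis concerns a level, the amount of energy used at rest. The named outcome is a unitless ratio of two gas volumes. A ratio drops the common scale of its parts, and here that scale carries most of the information about energy expenditure. RQ can stay still while expenditure falls, and it can move while expenditure is constant.

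An analyst following the SAP to the letter would fit the model to RQ and then have to say something about energy expenditure. A null result would not show that expenditure was unchanged, and a shift would not show that it rose or fell. If the team noticed this later and switched to kcal/day, that would be an outcome chosen after the plan was fixed.

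**Working it through.** **The plan's own figure.** The SAP states no effect size, SD or power for RQ or resting energy expenditure, so there is no figure on this point to reproduce. Its only sample-size result concerns the correlation between change in EEG arousals and change in leptin: "The detectable correlation is $r=-0.43$ for a sample size of 40". Two-sided Fisher z gives r = tanh((1.960 + 0.842)/√(40 − 3)) = 0.4306, which agrees. This is background only; nothing below depends on it.

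**Inputs.** From the documents: the hypothesis (resting energy expenditure falls) and the dependent measure (RQ). Assumed, because neither document supplies them:

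- RQ means respiratory quotient, VCO2/VO2.
- Energy expenditure (EE) is a positive weighted sum of the two gas volumes.
- The illustrative volumes are VO2 = 200 and VCO2 = 164 mL/min.

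**Algebra.** Write EE = a·VO2 + b·VCO2 with a, b > 0. Since VCO2 = RQ·VO2,

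EE = VO2 × (a + b·RQ).

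RQ alone leaves VO2 free, so it fixes neither the level of EE nor the direction of its change. If both gases are multiplied by a factor f, EE is multiplied by f and RQ is unchanged, whatever a and b are.

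**Check over coefficients.** Starting from VO2 = 200 and VCO2 = 170 (RQ 0.85), with three assumed pairs (a, b):

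| (a, b) | EE change, both gases −5% / −10% | RQ after | EE change, RQ 0.85→0.80 at fixed VO2 | VO2 that keeps EE constant at RQ 0.80 |
|---|---|---|---|---|
| (3.9, 1.1) | −5% / −10% | 0.85 | −1.1% | 202.3 |
| (3.0, 2.0) | −5% / −10% | 0.85 | −2.1% | 204.35 |
| (1, 1) | −5% / −10% | 0.85 | −2.7% | 205.56 |

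A rise in oxygen uptake of about 1.2% to 2.8% is therefore enough to hide a 0.05 drop in RQ completely.

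**Illustration in kcal/day.** With the assumed equation EE = 1.44 × (3.941·VO2 + 1.106·VCO2), volumes in mL/min:

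- Base: 1.44 × (3.941 × 200 + 1.106 × 164) = 1.44 × 969.584 = 1396.2 kcal/day, RQ 0.82.
- Both gases −5% (190/155.8): 1326.4 kcal/day, RQ 0.82. Both −10% (180/147.6): 1256.6 kcal/day, RQ 0.82.
- EE held at 1396.2, using VO2 = 1396.2/1.44/(3.941 + 1.106·RQ): RQ 0.75 needs 203.2/152.4 mL/min, and RQ 0.90 needs 196.4/176.8.
- EE down 5% to 1326.4: RQ 0.79 fits with 191.3/151.1, and RQ 0.85 fits with 188.7/160.4. The same fall in expenditure can come with RQ lower, unchanged or higher.
- VO2 fixed at 200: RQ 0.70 gives 1358.0 and RQ 1.00 gives 1453.5, a ratio of 1.070. Even that wide a swing in RQ moves EE by only 7.0%.

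**Range over starting volume.** At RQ 0.82, VO2 = 180 gives 1256.6 kcal/day, falling to 1193.8 (−5%) or 1130.9 (−10%). VO2 = 220 gives 1535.8, falling to 1459.0 or 1382.2. RQ stays at 0.82 throughout.

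**The case against.** The strongest reply is that RQ is loose shorthand. The SAP openly calls it an indirect measure, the protocol schedules an energy expenditure assessment, and the same sentence is loosely drafted elsewhere: it carries over terms for randomization order that the Hypothesis 1a text does not contain, and neither document describes a randomization. On that reading the team intends indirect calorimetry, would have kcal/day to hand, and has merely named the wrong variable. This is possible. But the sentence names RQ as the dependent measure, no energy expenditure variable appears anywhere, and calling the measure indirect supplies no conversion. If shorthand was meant, the same correction is needed.

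Three narrower objections have merit. First, neither document spells out RQ, so respiratory quotient is a reading, though the natural one beside resting EE. Second, the kcal figures are assumed throughout. They show what is possible, not what is likely in these women, and the algebra carries the argument. Third, the absence of energy expenditure from the endpoint lists is weak evidence, because those lists do not contain RQ either; the case rests on the hypothesis set against its named dependent measure.

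It is also fair that the hypothesis is exploratory and the proxy is labelled as such, which limits the weight of the point. Even so, an exploratory outcome has to measure what its hypothesis names.

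**Conclusion.** The point holds. As written, the SAP names no energy expenditure variable as the outcome for a hypothesis about energy expenditure, and the variable it does name cannot give the level of expenditure or the direction of its change. A proportional fall of any size leaves RQ exactly where it was.

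This rests on reading RQ as respiratory quotient and on energy expenditure being a positive weighted sum of the two gas volumes. It does not depend on the particular coefficients or volumes. How much information would be lost in this study cannot be stated, because the documents give no variability or expected change for either quantity. The effect is limited to Exploratory Hypothesis 1: the primary and secondary endpoints, the Aims 1–3 analyses and the sample size are untouched.

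**What to change.** In the SAP's text for Exploratory Hypothesis #1, name resting energy expenditure (kcal/day) as the dependent variable of the mixed model. State that it comes from the energy expenditure assessment in the Table of Procedures, and give the formula and the oxygen and carbon dioxide readings from which it is computed. Keep RQ as a separate exploratory outcome, described as substrate use.

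If only the ratio has been retained, reword the hypothesis in the protocol and its conclusion so that they concern substrate use and make no claim about energy expenditure.

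The cost is wording. No new procedure is needed if the gas readings were kept. That is an assumption, since the documents name no device or gas variable and the sleep block descriptions include no gas-exchange procedure, so confirm it before choosing between the two routes. No other analysis changes.
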